#### **Second Infusion (Day 15 of First Course)**

Patients who experienced infusion-related reactions to the first infusion should receive study drug as per the initial infusion schedule, with the rate of infusion not exceeding half that associated with the prior reactions. If this reduced rate is tolerated for 30 minutes, then the infusion rate may be increased to the next closest rate following the infusion schedule.

Patients who miss the allocated day (Day 15  $\pm$  1 day) for the second infusion (the first infusion will be administered following randomization on Day 1) will be contacted and another visit arranged as soon as practically possible in order to administer study drug. Such cases will be considered protocol deviations (see Section 3.13).

If a patient experiences a new infection or other AE between the Day 1 and Day 15 infusions of any treatment, the Day 15 infusion should be delayed until the infection or AE has completely resolved and the Investigator considers it safe to resume treatment. A maximum delay of 15 days from the scheduled date of the second infusion is permitted. Patients who have a delay of >15 days in receiving the second infusion due to an AE or otherwise will be discontinued from the study treatment.

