### **3.2.3 Study Drug Administration (Part B)**

Patients with active rheumatoid arthritis (<50% improvement from Baseline in both the swollen and tender joint counts) who have been followed up during Part A will be provided with continued (or additional) treatment of rituximab.

Before subsequent dose, absolute neutrophil count must be  $\geq 1.5 \times 10^9/L$  and platelet counts must be  $\geq 75 \times 10^9/L$ . If the Absolute Neutrophil Count (ANC) value and platelet count are marginally lower, re-testing at an unscheduled visit may be performed at the discretion of the Investigator within the 4-week period between Week 20 and Week 24. In case Visit 11 is missed, all safety evaluations including ANC value and platelet count must be completed as an unscheduled visit for patient to be eligible for second course of infusion.

Eligible patients in the SAIT101 arm will receive additional SAIT101 treatment at Week 24 and Week 26. Eligible patients in the MabThera® arm will receive additional MabThera® treatment at Week 24 and Week 26. Eligible patients in the Rituxan® arm will be randomized in a 1:1 ratio to receive SAIT101 or Rituxan® treatment at Week 24 and Week 26.

Patients who develop an infusion reaction during the second course of treatment should be managed as described in Section 3.2.1.

Patient who are not eligible for the second course of study drug will also attend all visits after Week 24.

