- g Posterior-anterior and lateral chest X-rays (or chest radiographs in accordance with local requirements) should be obtained and reviewed by the Investigator or designee. If chest radiographs taken within the past 3 months show no clinically significant abnormality, and there are no signs or symptoms suggestive of pulmonary disease that would exclude the patient from the study, then a chest radiograph does not need to be repeated. Chest X-rays may be repeated at any time during the study for suspected TB or chest infection.
- h Patients should rest for at least 5 minutes in a supine position before ECG evaluation.
- i In women of childbearing potential; serum pregnancy test (central laboratory) at Screening and EOS. Urine pregnancy test prior to each dose (first and second courses of treatment).
- j All patients except withdrawn patients will continue to attend visits until Week 52 regardless of the second course infusion to obtain PK / PD, safety, efficacy, and immunogenicity data.
- k Unscheduled visits should be scheduled as per Investigator discretion. Tests will be performed as per Investigator's discretion.
- l Study drug is required to be dispensed at Week 24 and Week 26, based on ANC value and platelet count at Week 20 and both the swollen and tender joint counts assessed at Week 24. If the ANC value and platelet count are marginally lower, re-testing at an unscheduled visit may be performed at the discretion of the Investigator within the 4-week period between Week 20 and Week 24. In case Visit 11 is missed, all safety evaluations including ANC value and platelet count must be completed as an unscheduled visit for patient to be eligible for second course of infusion.

- m SAIT101 or Rituxan® or MabThera® for intravenous infusion. On Days 1 and 15, each patient will receive one course of two 1,000 mg (10 mg/mL) drug infusions. Patients who, at Week 24, have a <50% improvement from Baseline in both the swollen and tender joint counts will be eligible for a further course of two 1,000 mg drug infusions. Eligible patients in the SAIT101 arm will receive the second course of SAIT101 treatment at Week 24 and Week 26. Eligible patients in the MabThera® arm will receive the second course MabThera® treatment at Week 24 and Week 26. Eligible patients in the Rituxan® arm will be randomized in a 1:1 ratio to receive SAIT101 or Rituxan® treatment at Week 24 and Week 26.

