To be eligible for the second course of treatment, patients must have an absolute neutrophil count (ANC)  $\geq 1.5 \times 10^3/\mu\text{L}$  and platelet counts  $\geq 75 \times 10^9/\text{L}$  observed at Week 20 (V11). If the ANC value and platelet count are marginally lower, re-testing at an unscheduled visit may be performed at the discretion of the Investigator within the 4-week period between Week 20 and Week 24. In case Visit 11 is missed, all safety evaluations including ANC value and platelet count must be completed as an unscheduled visit for patient to be eligible for second course of infusion.

Following must be performed in the unscheduled visit in this case:

- Neurological examination;
- Physical examination and vital signs;

- Documentation of concomitant medications;
- Assessment of AEs/SAEs/ADRs;
- Clinical chemistry, hematology, and urinalysis;

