### **3.6.1.3 Study Drug Administration Part B**

Patients with an inadequate response (<50% improvement from Baseline in both the swollen and tender joint counts) at Week 24 (Visit 12), will be eligible to receive a further course of two 1,000 mg i.v. infusions, one infusion at Week 24 (Day 1 of second course) and the second infusion at Week 26 (14 days after first dose of second course).

The following must be performed on **Day 169 ± 3 days (Week 24, Day 1 of the Second course of infusion)**:

Following must be performed:

- Physical examination and vital signs;
- Neurological examination;
- Documentation of concomitant medications;
- Assessment of AEs/SAEs/ADRs;
- Urine pregnancy test for applicable females administered the second course of the study drug;

The following efficacy assessments will be performed:

- Patient's assessment: global VAS and HAQ-DI, including patient's pain VAS;
- Physician's assessment: global VAS;
- Joint assessment. Each of the 66/68 joints will be evaluated for tenderness and swelling.

The following laboratory assessments will be performed:

- IgG, IgM, and IgA;

- Clinical chemistry, hematology, urinalysis and HBV DNA only when negative HBsAg and positive HbcAb at screening;
- CRP, ESR;
- PK and PD sampling;
- Immunogenicity.

The following must be also performed:

- Contact IXRS;
- Randomization;
- The first of the two infusions of the study drug (see Section 3.2.1), as per IXRS for eligible patients only.

The following must be performed on **Day 183 ± 3 days (Week 26, Day 15 of the Second course of infusion)**:

- Physical examination and vital signs
- Neurological examination;
- Documentation of concomitant medications;
- Assessment of AEs/SAEs/ADRs;
- Urine pregnancy test for applicable females administered the second course of the study drug;
- Contact IXRS;
- The second of the two infusions of study drug (see Section 3.2.1), as per IXRS, for eligible patients only.

The following assessments will be performed on **Day 253 ± 7 days (Week 36)**:

- Physical / Neurological examination;
- Document concomitant medications;

- Assessment of AEs/SAEs/ADRs.

The following efficacy assessments will be performed:

- Patient's assessment: global VAS and HAQ-DI, including patient's pain VAS;
- Physician's assessment: global VAS;
- Joint assessment. Each of the 66/68 joints will be evaluated for tenderness and swelling.

Laboratory assessments

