### **3.7.3 Individual Patient**

If a patient discontinues the study treatment prematurely, the reason given must be fully evaluated and recorded appropriately in the source documents and the patient's eCRF. If the patient is discontinued from study treatment because of an AE, that AE should be indicated as the reason for discontinuation.

The Investigator can discontinue treatment of a patient at any time if medically necessary. In addition, patients meeting the patient discontinuation criteria must be discontinued from the study treatment.

Patients will be discontinued from the study treatment in the following circumstances:

- A patient who does not meet the enrolment criteria is inadvertently randomized, that patient must be discontinued from study treatment and the Sponsor or Clinical Research Organization (CRO) must be contacted.
- The Investigator decides that the patient should be discontinued from study treatment. If this decision is made because of an intolerable AE or a clinically significant laboratory value, the study drug is to be discontinued and appropriate measures are to be taken. The Sponsor or designee is to be notified immediately.
- Patient non-compliance, defined as refusal or inability to adhere to the study schedule or procedures (see Section 3.12).
- Treatment with a prohibited concomitant medication other than the use of appropriate medications for the treatment of AEs under the direction of the Sponsor and/or Investigator or Sub-investigator
- Lack of efficacy. Subjects who lack efficacy can be included in the PK and efficacy analysis. Patients receiving rescue therapy prior to Week 24 would not be eligible for second course of infusion.
- Patients who meet any of the following specific safety discontinuation criteria, however can be included for the PK analysis:
  - Patients who develop severe infusion-related reactions, especially severe dyspnea, bronchospasm or hypoxia, should have the infusion interrupted immediately to receive aggressive symptomatic treatment. In all patients, the infusion should not be restarted on the same day until complete resolution of all symptoms. At this time, the infusion may be initially resumed at the discretion of the Investigator at not more than one-half the previous rate. If the same ADRs occur for a second time, the infusion should be permanently discontinued.
  - Active TB

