  - Invasive fungal infection or opportunistic infection including, but not limited to, listeriosis, legionellosis or pneumocystis.
  - Hepatitis B virus reactivation, in some cases resulting in fulminant hepatitis, or hepatic failure

- Any other AEs which, in the opinion of the Investigator or the Sponsor, could compromise the patient's safety or well-being if they continue to participate in the study.
- PML. Neurological warning signs include: major changes in vision, unusual eye movements; loss of balance or coordination; and disorientation or confusion
- Cancer: any malignant lesion. Patients with basal cell and squamous cell carcinomas of the skin or carcinoma in situ of the cervix uteri that has been excised and cured, may be continued on the study at the discretion of the Investigator.
- Pregnancy in a female participant
- Patient lost to follow-up despite reasonable efforts to make contact with the patient
- Patients who have a delay of >15 days in receiving the second infusion due to an AE or otherwise
- Judgment by the Investigator or Sub-investigator that study treatment discontinuation is necessary for reasons other than those described above.

To prevent missing data in important supportive efficacy and safety analysis, patients who discontinued study drug, will also attend all visits until week 52.

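### Table 2 footnote l releases the Week 26 infusion on the Week 20 blood count, while Section 3.2.3 probably applies the same limits to every dose; the newer Week 24 count has no stated role

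*Protocol*

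**What the plan says.** Three places in the protocol set the ANC and platelet condition for the second course.

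- **Table 2, footnote l**, attached to the IXRS contact at both Week 24 and Week 26: "Study drug is required to be dispensed at Week 24 and Week 26, based on ANC value and platelet count at Week 20", together with the Week 24 joint counts. A marginally low count may be re-tested between Week 20 and Week 24. A missed Visit 11 must be replaced by an unscheduled visit.
- **Section 3.6.1.2** (end of the Week 20 list): "To be eligible for the second course of treatment, patients must have an absolute neutrophil count (ANC") and a platelet count at or above the limits at Week 20. This is a condition on the course as a whole.
- **Section 3.2.3**: "Before subsequent dose, absolute neutrophil count must be" at least 1.5 × 10⁹/L, with platelets at least 75 × 10⁹/L. The sentence names no visit. The sentences after it repeat the Week 20 to Week 24 re-test and the missed-visit rule.

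Hematology is drawn again at Week 24; the Section 3.6.1.3 list includes "Clinical chemistry, hematology, urinalysis and HBV DNA only when negative HBsAg and positive HbcAb at screening". The list for "Day 183 ± 3 days (Week 26, Day 15 of the Second course of infusion") contains no hematology, and neither does the Week 26 column of Table 2.

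**The concern.** Footnote l is the only place that says which count releases the Week 26 drug, and it points to Week 20 or to a replacement count obtained before Week 24. By Week 26 a newer count has been drawn, and no numeric rule is attached to it by name.

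The two rules therefore differ when the Week 20 count passes and the Week 24 count does not. Under footnote l the drug is released. Under Section 3.2.3, read as covering each infusion, it should not be. Different sites can follow different sentences and each believe it is compliant. What is at stake is the safety of some Part B patients, who would receive a further 1,000 mg although the newest count on file is below the limit that the protocol itself set for the second course.

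**Working it through.** The plan states no figure to reproduce. The check compares the texts and then does the visit-day arithmetic.

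**1. Are the limits the same everywhere?** Yes. Section 3.6.1.2 gives ANC in 10³/µL and Section 3.2.3 gives it in 10⁹/L; 1.5 × 10³/µL = 1.5 × 10⁹/L. The platelet limit is identical.

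**2. Does Section 3.2.3 reach Week 26?** Probably. The protocol generally uses dose for one infusion and course for the pair: Table 2 footnote i (pregnancy test ahead of each dose in both courses), Section 3.6.1.3 (Week 26 is dated from the first dose of the second course), Section 3.12 (a missed second infusion is a missed dose) and Section 6.2.1.1 (both planned doses). The sentence still does not say which sample counts.

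**3. How old is each count?** Visit days from Table 2: Week 20 = 141 ± 3, Week 24 = 169 ± 3, Week 26 = 183 ± 3.

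| Count used | Infusion | Nominal age (days) | With windows (days) |
|---|---|---|---|
| Week 20 | Week 24 | 169 − 141 = 28 | (166 − 144) = 22 to (172 − 138) = 34 |
| Week 20 | Week 26 | 183 − 141 = 42 | (180 − 144) = 36 to (186 − 138) = 48 |
| Re-test, Day 141 to 169 | Week 26 | 183 − 169 = 14 to 183 − 141 = 42 | not computed |
| Week 24 | Week 26 | 183 − 169 = 14 | (180 − 172) = 8 to (186 − 166) = 20 |

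**4. What already protects a patient with a low Week 24 count?**

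- Section 5.7: the Investigator reviews every result, and a clinically significant change from Baseline is an AE. That judgment need not be made the first time an abnormal value is seen.
- Section 3.2.2: "If a patient experiences a new infection or other AE between the Day 1 and Day 15 infusions of any treatment", the later infusion is delayed until the event resolves, for at most 15 days. The heading refers to the first course, but the sentence extends to any treatment.
- Section 3.7.3: "If this decision is made because of an intolerable AE or a clinically significant laboratory value, the study drug is to be discontinued".
- Section 3.7.3 also discontinues treatment for "Patients who have a delay of >15 days in receiving the second infusion due to an AE or otherwise".

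The first three depend on clinical judgment or on an AE, and the fourth acts only once a delay exceeds 15 days. What remains is a Week 24 count below 1.5 or 75 × 10⁹/L that the Investigator has not judged clinically significant.

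**5. Would a hold fit the schedule?** A 15-day hold from Day 183 ends on Day 198, or on Day 186 + 15 = 201 from the end of the window. The earliest Week 36 visit is Day 253 − 7 = 246, so at least 246 − 201 = 45 days remain.

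**The case against.** The case for leaving the text alone has four main parts.

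- **A numeric rule already exists.** Section 3.2.3 is a mandatory sentence in the body text, and on the protocol's vocabulary it covers Week 26. This stands. A reader might infer from footnote l that nothing numeric protects the Week 26 infusion; the documents do not support that. The defect is that footnote l and Section 3.2.3 disagree about what governs release.
- **The first course works the same way.** Exclusion criterion 16 applies its limits at Screening, up to 30 days before Day 1. Hematology is drawn on Day 1 and Day 15 with no numeric limit attached. The qualifying count can therefore be 30 + 14 = 44 days old at Day 15 (45 with the one-day window), close to the 42 days here. One check per course may be deliberate. This also stands, but it does not explain the wording of Section 3.2.3. If one check is intended, that sentence should say so.
- **The Week 24 sample also predates the second course.** The visit sequence in Section 3.6.1 puts laboratory work ahead of pre-medication and study drug. A reader might take the Week 24 count as evidence of how the patient tolerated the first infusion of the course; it is not. It is only a newer pre-course value, and a re-test on Day 169 would be equally old.
- **Release may be controlled in documents not seen here.** The IXRS manual, or the re-treatment CRF page from which SAP Section 8 takes Part B eligibility, may hold a further check. That is possible, but it would not align the two protocol texts.

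**Conclusion.** The point holds as a minor inconsistency in Part B dosing rules, worth correcting because correction is cheap. The residual gap is narrow: Week 20 count acceptable, Week 24 count below a limit, Investigator does not consider it clinically significant, and the site follows footnote l.

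Its frequency is unknown, because the documents give no rate of low Week 24 counts. The only measurable size is the age of the governing count, 42 days against 14.

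Two stronger readings might be inferred and should not be. The first is that patients with clinically significant cytopenia would be dosed regardless; Sections 5.7, 3.2.2 and 3.7.3 already address them. The second is that the trial's conclusions are at risk. The PK sampling behind the primary endpoints and the main efficacy assessment both finish at Week 24, before the Week 26 infusion.

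The conclusion rests on reading dose as a single infusion. If the sponsor meant the whole course, there is no conflict in intent, but Section 3.2.3 still needs rewording.

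**What to change.** **Footnote l.** Separate the two visits:

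- Week 24 dispensing depends on the Week 20 count (or the re-test or replacement visit) and the Week 24 joint counts.
- Week 26 dispensing depends on the most recent available ANC and platelet count, normally Week 24, meeting the same limits.
- If that count is low, hold the infusion and re-test at an unscheduled visit, under the existing 15-day maximum delay and discontinuation rule.
- If the Week 24 result is missing, obtain a count at an unscheduled visit before or at Week 26 where feasible. Otherwise the last available count may be used at the Investigator's discretion, so that a lost sample alone does not cost the patient an infusion.

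**Section 3.2.3.** Replace the opening words of the sentence with: *Before each infusion of the second course, the most recent available*. The limits stay as they are.

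**Cost.** Protocol wording only. The Week 24 sample and the Week 26 IXRS contact are already scheduled, so extra tests arise only when a result is low or missing. No new discontinuation rule is needed. A few second infusions will be delayed or missed, leaving slightly fewer complete second courses in the transition data. The change assumes Week 24 results are back before Week 26, within 8 days in the tightest case. The documents give no turnaround time, and hematology is taken to be central because Table 3 lists only ESR and the urine pregnancy test as local.

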### **3.6.1 Schedule of Assessments**

The sequence of assessments at each visit will be standardized as follows (at visits as required by the schedule of assessments):

1. At Visit 1 (Screening): Obtaining of informed consent
2. General assessments: Physical examination, Neurological examination, and Vital signs
3. Efficacy assessments: Patient-reported assessments (patient pain VAS, global VAS, and HAQ-DI)
4. Efficacy assessments: Investigator assessments (swollen and tender joint counts, physician's global assessment of disease activity VAS, EULAR, DAS28)
5. Laboratory/Safety assessments
6. PK/PD/immunogenicity assessments, where applicable
7. If applicable, pre-medication and study drug

All assessments will be performed prior to administration of pre-medication, unless otherwise specified.

Patient-reported data (pain VAS, global VAS, HAQ-DI) should be recorded by the patient on the relevant source documents. In special circumstances when the patient has difficulty writing or is unable to read, the study personnel or patient representative can record this data on behalf of the patient and based on responses provided by the patient verbally. The procedure followed must be documented clearly in the patient notes.

#### **3.6.1.1 Screening Period**

##### **Visit 1 (-30 days and not to exceed 60 days before Day 1)**

Patients must have the ability and willingness to provide written informed consent (prior to any study-specific procedures being performed) and to comply with the requirements of the protocol. All the Screening assessments should be performed within 30 days prior to randomization on Day 1 (Visit 2, Baseline).

However, in patients who require a washout of current anti-TNF medication or other biologic and non-biologic DMARD treatment (except MTX) the Screening period may be extended to allow for the washout required, but will not exceed 60 days. In these patients all Screening assessments must be performed within 30 days prior to randomization with the exception of the informed consent and chest X-ray.

Once the patient has provided written informed consent and meets the inclusion and exclusion criteria (see Section 3.4), the study center will register the patient in the IXRS.

The following must also be performed:

- Document patient's demographic information (including gender, date of birth and, when possible per local regulations, race), and medical and surgical history (including RA history);
- Physical examination, including height (cm) and weight (kg);
- Neurological examination (for signs and symptoms of PML);
- Chest X-ray, unless taken within the previous 3 months;
- Serum pregnancy test;
- Vital signs;
- Document previous and concomitant medications (including vaccination history);
- Resting 12-lead ECG.

The following safety/laboratory assessments will be performed:

- QuantiFERON® TB- Gold test;
- Serology (HBsAg and HBcAb, HBV DNA by PCR [ $<20$  IU/mL or 112 copies/mL], anti-HCV, and HIV test), IgG, IgM, IgA, clinical chemistry, hematology, and urinalysis;
- CRP, ESR;
- RF.

